11.3 Reporting to the Institutional Review Board (IRB)

Investigative sites within DF/HCC will report all serious adverse events directly to the DFCI Office for Human Research Studies (OHRS).

11.4 Reporting to the Food and Drug Administration (FDA)

The DF/HCC Overall Principal Investigator, as holder of the IND, will be responsible for all communication with the FDA. The DF/HCC Overall Principal Investigator will report to the FDA, regardless of the site of occurrence, any adverse event that is serious, unexpected and reasonably related (i.e., possible, probable, definite) to the study treatment.

CONFIDENTIAL

This document is confidential. Do not disclose or use except as authorized.

Unexpected fatal or life-threatening experiences associated with the use of the study treatment will be reported to FDA as soon as possible but in no event later than 7 calendar days after initial receipt of the information.

All other serious unexpected experiences associated with the use of the study treatment will be reported to FDA as soon as possible but in no event later than 15 calendar days after initial receipt of the information.

Events will be reported to the FDA by telephone ([name]) or by fax ([name]) using Form FDA 3500A (Mandatory Reporting Form for investigational agents) or FDA Form 3500 (Voluntary Reporting Form for commercial agents). Forms are available at <http://www.fda.gov/medwatch/getforms.htm>.

11.5 Reporting to Hospital Risk Management

Participating investigators will report to their local Risk Management office any participant safety reports or sentinel events that require reporting according to institutional policy.

11.6 Pregnancy Reporting

If a woman becomes pregnant or suspects that she is pregnant while participating in this study, she must inform the investigator immediately and permanently discontinue study drug. The sponsor-investigator must immediately fax a completed Pregnancy Form to the Millennium Department of Pharmacovigilance or designee (see Section 11.2). The pregnancy must be followed for the final pregnancy outcome.

If a female partner of a male patient becomes pregnant during the male patient's participation in this study, the sponsor-investigator must also immediately fax a completed Pregnancy Form to the Millennium Department of Pharmacovigilance or designee (see Section 11.2). Every effort should be made to follow the pregnancy for the final pregnancy outcome.

11.7 Monitoring of Adverse Events and Period of Observation

All adverse events, both serious and non-serious, and deaths that are encountered from initiation of study intervention, throughout the study, and within 30 days of the last study intervention should be followed to their resolution, or until the participating investigator assesses them as stable, or the participating investigator determines the event to be irreversible, or the participant is lost to follow-up. The presence and resolution of AEs and SAEs (with dates) should be documented on the appropriate case report form and recorded in the participant's medical record to facilitate source data verification.

For some SAEs, the study sponsor ([name]) or designee may follow-up by telephone, fax, and/or monitoring visit to obtain additional case details deemed necessary to appropriately evaluate the SAE report (e.g., hospital discharge summary, consultant report, or autopsy report).

CONFIDENTIAL

This document is confidential. Do not disclose or use except as authorized.

Participants should be instructed to report any serious post-study event(s) that might reasonably be related to participation in this study.

11.8 Product Complaints

A product complaint is a verbal, written, or electronic expression that implies dissatisfaction regarding the identity, strength, purity, quality, or stability of a drug product. Individuals who identify a potential product complaint situation should immediately contact MedComm Solutions (see below) and report the event. Whenever possible, the associated product should be maintained in accordance with the label instructions pending further guidance from a Millennium Quality representative.

**For Product Complaints,
call MedComm Solutions at
[contact] ([name])
(US and International)**

Product complaints in and of themselves are not AEs. If a product complaint results in an SAE, an SAE form should be completed and sent to Millennium Pharmacovigilance (refer to Section 8.2).

12. DATA AND SAFETY MONITORING

12.1 Data Reporting

12.1.1 Method

The QACT will collect, manage, and monitor data for this study.

12.1.2 Data Submission

The schedule for completion and submission of case report forms (paper or electronic) to the QACT is as follows:

Form	Submission Timeline
Eligibility Checklist	Complete prior to registration with QACT
On Study Form	Within 14 days of registration
Baseline Assessment Form	Within 14 days of registration
Treatment Form	Within 10 days of the last day of the cycle
Adverse Event Report Form	Within 10 days of the last day of the cycle
Response Assessment Form	Within 10 days of the completion of the cycle required for response evaluation
Off Treatment/Off Study Form	Within 14 days of completing treatment or being taken off study for any reason

CONFIDENTIAL

This document is confidential. Do not disclose or use except as authorized.

Follow up/Survival Form	Within 14 days of the protocol defined follow up visit date or call
-------------------------	---

12.2 Safety Meetings

The DF/HCC Data and Safety Monitoring Committee (DSMC) will review and monitor toxicity and accrual data from this trial. The committee is composed of clinical specialists with experience in oncology and who have no direct relationship with the study. Information that raises any questions about participant safety will be addressed with the Principal Investigator and study team.

The DSMC will meet quarterly and/or more often if required to review toxicity and accrual data. Information to be provided to the committee may include: up-to-date participant accrual; current dose level information; DLT information; all grade 2 or higher unexpected adverse events that have been reported; summary of all deaths occurring within 30 days for Phase I or II protocols; for gene transfer protocols, summary of all deaths while being treated and during active follow-up; any response information; audit results, and a summary provided by the study team. Other information (e.g. scans, laboratory values) will be provided upon request.

12.3 Monitoring

Involvement in this study as a participating investigator implies acceptance of potential audits or inspections, including source data verification, by representatives designated by the DF/HCC Overall Principal Investigator (or Protocol Chair) or DF/HCC. The purpose of these audits or inspections is to examine study-related activities and documents to determine whether these activities were conducted and data were recorded, analyzed, and accurately reported in accordance with the protocol, institutional policy, Good Clinical Practice (GCP), and any applicable regulatory requirements.

All data will be monitored for timeliness of submission, completeness, and adherence to protocol requirements. Monitoring will begin at the time of participant registration and will continue during protocol performance and completion.

13. REGULATORY CONSIDERATIONS

13.1 Protocol Review and Amendments

This protocol, the proposed informed consent and all forms of participant information related to the study (e.g., advertisements used to recruit participants) and any other necessary documents must be submitted, reviewed and approved by a properly constituted IRB governing each study location.

Any changes made to the protocol must be submitted as amendments and must be approved by the IRB prior to implementation. Any changes in study conduct must be reported to the

CONFIDENTIAL

This document is confidential. Do not disclose or use except as authorized.

IRB. The DF/HCC Overall Principal Investigator (or Protocol Chair) will disseminate protocol amendment information to all participating investigators.

All decisions of the IRB concerning the conduct of the study must be made in writing.

13.2 Informed Consent

All participants must be provided a consent form describing this study and providing sufficient information for participants to make an informed decision about their participation in this study. The formal consent of a participant, using the IRB approved consent form, must be obtained before the participant is involved in any study-related procedure. The consent form must be signed and dated by the participant or the participant's legally authorized representative, and by the person obtaining the consent. The participant must be given a copy of the signed and dated consent document. The original signed copy of the consent document must be retained in the medical record or research file.

13.3 Ethics and Good Clinical Practice (GCP)

This study is to be conducted according to the following considerations, which represent good and sound research practice:

- US Code of Federal Regulations (CFR) governing clinical study conduct and ethical principles that have their origin in the Declaration of Helsinki
 - Title 21 Part 50 – Protection of Human Subjects
www.access.gpo.gov/nara/cfr/waisidx_02/21cfr50_02.html
 - Title 21 Part 54 – Financial Disclosure by Clinical Investigators
www.access.gpo.gov/nara/cfr/waisidx_02/21cfr54_02.html
 - Title 21 Part 56 – Institutional Review Boards
www.access.gpo.gov/nara/cfr/waisidx_02/21cfr56_02.html
 - Title 21 Part 312 – Investigational New Drug Application
www.access.gpo.gov/nara/cfr/waisidx_02/21cfr312_02.html
- State laws
- DF/HCC research policies and procedures:
<http://www.dfhcc.harvard.edu/clinical-research-support/clinical-research-unit-cru/policies-and-procedures/>

It is understood that deviations from the protocol should be avoided, except when necessary to eliminate an immediate hazard to a research participant. In such case, the deviation must be reported to the IRB according to the local reporting policy.

13.4 Study Documentation

The investigator must prepare and maintain adequate and accurate case histories designed to record all observations and other data pertinent to the study for each research participant. This information enables the study to be fully documented and the study data to be subsequently verified.

CONFIDENTIAL

This document is confidential. Do not disclose or use except as authorized.

Original source documents supporting entries in the case report forms include but are not limited to hospital records, clinical charts, laboratory and pharmacy records, recorded data from automated instruments, microfiches, photographic negatives, microfilm or magnetic media, and/or x-rays.

13.5 Records Retention

All study-related documents must be retained for the maximum period required by applicable federal regulations and guidelines or institutional policies.

13.6 IND Annual Reports

The sponsor investigator or his designee will submit the annual report for this PI-initiated trial within 60 days of the IND anniversary date in accordance with 21 CFR 312.33. The data elements that are to be submitted in the report are provided in 21 CFR 312.33. The Annual Report should be filed in the study's Regulatory Binder.

14. STATISTICAL CONSIDERATIONS

14.1 Study Design/Endpoints

Following Fleming's single phase approach and with a one-sided alpha set at 0.05 and beta at 0.20 (80% power) assuming a null VGPR or better of 18% and a successful VGPR or better of 40%, we will need to accrue 23 participants. In a previous study, the combination of bortezomib, rituximab and dexamethasone induced VGPR or better of 35% [22]. If at least 9 participants are found to have a response of VGPR or better, the trial will be deemed a success and IDR will warrant further testing in patients with WM. Accounting for 10% of non-evaluable patients, the total sample size will be 26 patients. In addition, with a sample size of 26 participants, the probability of observing at least one adverse event will be 93% when the actual probability of this event is 10%. Counting 1 patient who was registered but never started, 27 patients were accrued to this study.

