14.2 Populations for analysis

The population for all safety analyses is the Safety Analysis Set (SAS). All participants who receive at least one dose of any test material during the study will be included in the SAS population and included in the safety analysis.

Participants will be included in the Full Analysis Set (FAS) for the primary assessment of efficacy. The FAS will include those participants who have measurable disease present at baseline, have received at least one cycle of therapy, and have had their disease re-evaluated.

CONFIDENTIAL

This document is confidential. Do not disclose or use except as authorized.

The Per-Protocol Analysis Set (PPS) is defined as all participants from the FAS set who complete the study and are deemed to be protocol-compliant. To be protocol-compliant, a participant must not have any major protocol deviations during the study period. Protocol deviations will be identified prior to database lock and will be listed in the clinical study report. The PPS will be used for a secondary assessment of efficacy endpoints.

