14.8 Sample Size/Accrual Rate

CONFIDENTIAL

This document is confidential. Do not disclose or use except as authorized.

Following Fleming's single phase approach and with a one-sided alpha set at 0.05 and beta at 0.20 (80% power) assuming a null VGPR or better of 18% and a successful VGPR or better of 40%, we will need to accrue 30 participants. In a previous study, the combination of bortezomib, rituximab and dexamethasone induced VGPR or better of 35% [22]. If at least 10 participants are found to have a response of VGPR or better, the trial will be deemed a success and IDR will warrant further testing in patients with WM. Accounting for 10% of non-evaluable patients, the total sample size will be 33 patients. In addition, with a sample size of 33 participants, the probability of observing at least one adverse event will be 97% when the actual probability of this event is 10%.

The accrual expectation is 2-3 patients per month with a total accrual time of 12-15 months.

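### Sections 14.1 and 14.8 set different sample sizes and success cut-offs for the same hypotheses, and the 14.1 rule has at most 77% exact power, not 80%

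*Combined protocol and SAP*

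**What the plan says.** Sections 14.1 and 14.8 both invoke Fleming's single-stage method with one-sided alpha 0.05, 80% power, a null rate of VGPR or better of 18% and a target rate of 40%. They then give different designs.

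- **Section 14.1:** "we will need to accrue 23 participants"; "If at least 9 participants are found to have a response of VGPR or better, the trial will be deemed a success"; after a 10% allowance for non-evaluable patients, "the total sample size will be 26 patients". It also reports accrual: "Counting 1 patient who was registered but never started, 27 patients were accrued to this study".
- **Section 14.8:** "we will need to accrue 30 participants"; "If at least 10 participants are found to have a response of VGPR or better, the trial will be deemed a success"; after the same 10% allowance, "the total sample size will be 33 patients".

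Section 14.2 fixes the denominator: "Participants will be included in the Full Analysis Set (FAS) for the primary assessment of efficacy". Membership requires measurable disease at baseline, at least one cycle of therapy and a re-evaluation, so the FAS cannot exceed the 26 who started treatment.

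**The concern.** One primary endpoint has two success thresholds in force. With exactly 9 participants at VGPR or better, the declared conclusion depends on which section is read. The trial is single-arm and open-label and its accrual is complete, so an unresolved choice between 9 and 10 could be made with the results in view.

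The second problem lies within 14.1. Its number of participants and its cut-off do not come from the same calculation, and together they give less than the stated power. A negative result would be read against a 20% chance of missing a true 40% rate when the real chance is higher.

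**Working it through.** **Inputs** (14.1 and 14.8): p0 = 0.18, p1 = 0.40, one-sided alpha 0.05, power 0.80. Treated: 27 − 1 = 26 (14.1).

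**Step 1. Reproduce the 23.** The one-sample normal approximation is

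n = [(z_alpha·√(p0(1−p0)) + z_beta·√(p1(1−p1))) / (p1−p0)]²
= [(1.645·√(0.18·0.82) + 0.842·√(0.40·0.60)) / 0.22]²
= [(0.6319 + 0.4123) / 0.22]² = 22.53, so 23.

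Approximate power at 23 is 80.6%. Then 23/0.9 = 25.6, so 26. The 23 and the 26 in 14.1 are therefore correct by this method.

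**Step 2. Find the cut-off that goes with 23.** The same approximation rejects above

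n·p0 + 1.645·√(n·p0(1−p0)) = 4.14 + 1.645·√3.3948 = 7.17,

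which means at least 8. Section 14.1 says at least 9.

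**Step 3. Exact operating characteristics.** For cut-off r and n evaluable, alpha = P(X ≥ r) with X ~ Bin(n, 0.18), and power is the same tail with X ~ Bin(n, 0.40). Each cell shows alpha / power.

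| Evaluable | at least 8 | at least 9 | at least 10 |
|---|---|---|---|
| 22 | 0.032 / 71.0% | 0.010 / 54.6% | – |
| 23 | 0.042 / 76.3% | 0.014 / 61.2% | 0.004 / 44.4% |
| 24 | 0.053 / 80.8% | 0.019 / 67.2% | 0.006 / 51.1% |
| 25 | 0.066 / 84.6% | 0.025 / 72.7% | 0.008 / 57.5% |
| 26 | 0.081 / 87.8% | 0.033 / 77.5% | 0.011 / 63.6% |
| 27 | 0.098 / 90.5% | 0.041 / 81.6% | 0.015 / 69.1% |
| 30 | – | 0.076 / 90.6% | 0.032 / 82.4% |

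Power for at least 9 of 26 is 0.7745 before rounding, hence 77%.

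**Step 4. Search for a valid rule.** Taking at each n from 15 upward the smallest cut-off with exact alpha of 0.05 or less, the first n with power of at least 80% is 27, with a cut-off of 9 (0.041 / 81.6%). No cut-off meets both limits at 15 to 26 evaluable. The 14.8 pair, at least 10 of 30, meets its own claim (0.032 / 82.4%).

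**Step 5. How often the two cut-offs disagree.** They differ only at X = 9, whose probability is the difference between adjacent tails. At a 40% rate this is 0.6116 − 0.4438 = 16.8% with 23 evaluable and 0.7745 − 0.6358 = 13.9% with 26. At 18% it is 0.0142 − 0.0041 = 1.0% and 0.0326 − 0.0114 = 2.1%.

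**Step 6. Planning-stage view.** Suppose each of 26 treated is evaluable with probability 0.9, independently of the others and of response. The probability that fewer than 23 are evaluable is 26%. Evaluable responders follow Bin(26, 0.9p), which gives overall alpha 0.017 and power 63%. Once the FAS is known, the row for that number replaces this average.

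**The case against.** The best reply is that 14.8 is leftover text. The accrual sentence in 14.1 matches its own total of 26, and the 33 in 14.8 was never reached. The cut-off of 10 also belongs to 30 evaluable, so applying it to 26 or fewer is strained, and the two rules disagree at a single count. All of this is reasonable, and 14.1 probably does govern. But that is an inference: 14.8 is the section titled for sample size, it carries its own success rule, and no text marks it as superseded.

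On power, the 80% is a target fed into an approximate method, and part of the gap is approximate against exact calculation: even at least 8 of 23 has only 76% exact power. At 24 to 26 evaluable, 9 is also the smallest cut-off that holds exact alpha at or below 0.05, so it is a sound rule at those numbers. If all 26 are evaluable the shortfall is only about 2.5 points. These points stand, and they limit the weight of the power error. They do not rescue the stated figure, because no FAS that 26 treated can supply gives the 14.1 rule 80% power.

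It is also true that false positives are controlled and that section 14.7 calls for 95% confidence intervals, so a negative result need not be judged on planned power alone.

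**Conclusion.** The concern holds on both parts. The conflict between 14.1 and 14.8 must be fixed, because it leaves the primary success criterion undetermined at 9 responders. If the true rate is 40%, that count has a probability of about 14% to 17% with 23 to 26 evaluable.

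The power error is secondary and conservative. Under the 14.1 rule the chance of missing a true 40% rate is about 23% with 26 evaluable and 39% with the planned 23, against the stated 20%. These figures rest on exact binomial tails at the protocol's own 18% and 40% and on a FAS of no more than 26. The FAS number itself is not given, and fewer than 23 evaluable would lower power further (55% at 22).

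**What to change.** 1. Confirm which section governs, citing the approved amendment and its date. Section 13.1 already requires IRB approval before a change is implemented, and a dated record prevents the cut-off from being chosen with results known. If a result has already been declared, document which rule was applied.
2. Keep one sample-size paragraph and one cut-off, and delete or align the other.
3. If 14.1 governs, keep the cut-off of 9 and replace the 80% claim with the exact alpha and power for the confirmed FAS number, taken from the at-least-9 column. Do not lower the cut-off to 8 after accrual: its exact alpha exceeds 0.05 at 24, 25 and 26 evaluable.
4. If 14.8 governs, state that 26 treated cannot supply its 30 evaluable participants, and report alpha and power for at least 10 at the number obtained.
5. For clarity, name the FAS beside the cut-off. Section 14.2 already makes it the primary efficacy set.

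The cost is protocol and SAP wording only, with no added patients. If 14.1 is kept, the stated power falls from 80% to at most 77%.

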14.2 Populations for analysis

The population for all safety analyses is the Safety Analysis Set (SAS). All participants who receive at least one dose of any test material during the study will be included in the SAS population and included in the safety analysis.

Participants will be included in the Full Analysis Set (FAS) for the primary assessment of efficacy. The FAS will include those participants who have measurable disease present at baseline, have received at least one cycle of therapy, and have had their disease re-evaluated.

CONFIDENTIAL

This document is confidential. Do not disclose or use except as authorized.

The Per-Protocol Analysis Set (PPS) is defined as all participants from the FAS set who complete the study and are deemed to be protocol-compliant. To be protocol-compliant, a participant must not have any major protocol deviations during the study period. Protocol deviations will be identified prior to database lock and will be listed in the clinical study report. The PPS will be used for a secondary assessment of efficacy endpoints.

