1.3 Secondary Objectives

- To evaluate the rate of CR, partial response (PR), minimal response (MR), stable disease (SD) and progressive disease (PD)
- To evaluate the PFS, disease-free survival (DFS), time to progression (TTP), duration of response (DOR) and time to next therapy (TTNT)
- To evaluate the attainment of response, and depth of response (VGPR or better) and expression of MYD88 L265P and CXCR4-WHIM mutations in WM.
- To determine changes in MYD88 L265P burden in response to IDR in patients with WM using real-time quantitative PCR.
- To evaluate the FcγRIIIA-158 polymorphisms as surrogate markers for response to IDR in WM.

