14.7 Efficacy Analyses

Primary and secondary analyses will be performed in both the FAS and PPS populations and will include calculating the proportion of patients having an overall response (MR or better) and major response (CR or VG). Confidence intervals (95%) about these point estimates will be presented. Time to progression (TTP) and time to next therapy (TNT) as defined in sections 10.4, and 10.5, respectively will be estimated using Kaplan and Meier methodology with median time plus 25th and 75th percentile time to progression free survival along with 95% confidence intervals being provided, as appropriate. In addition, landmark analysis for 2 and 4 year progression free survival will be performed.

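### The response rate is planned only in patients with one cycle and a re-evaluation, so treated early drop-outs leave the denominator; an all-treated rate should be reported beside it

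*Combined protocol and SAP*

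**What the plan says.** Section 14.2 defines three sets. The safety set holds everyone who took any study treatment and is assigned to safety analyses. The FAS is the set for primary efficacy; its members must have measurable disease at baseline, "have received at least one cycle of therapy, and have had their disease re-evaluated". For the third, "The Per-Protocol Analysis Set (PPS) is defined as all participants from the FAS set who complete the study and are deemed to be protocol-compliant"; its role is that "The PPS will be used for a secondary assessment of efficacy endpoints".

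Section 14.7 then states: "Primary and secondary analyses will be performed in both the FAS and PPS populations". The response proportions with 95% intervals follow, then time to progression (TTP) and time to next therapy, and finally "landmark analysis for 2 and 4 year progression free survival will be performed". No response rate in all treated patients is planned. Section 14.12 says everyone in the study will be assessed for response, but it names no denominator and gives no rule for a patient without an assessment.

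Section 14.1 plans 23 evaluable patients, a success rule of 9 or more with VGPR or better, and this allowance: "Accounting for 10% of non-evaluable patients, the total sample size will be 26 patients". It also records that 27 were accrued, of whom one never started.

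**The concern.** Entry to the FAS depends on what happens after the first dose. Patients who stop during the first cycle, or before any re-evaluation, do so because of toxicity, early progression, death or withdrawal. They are unlikely to have done well, and someone never re-evaluated cannot be a documented responder. Removing such patients takes non-responders out of the denominator and leaves the numerator alone, so the reported rate and both confidence limits move up. Chance does not offset this, because the direction is the same for every such patient. At stake is the headline estimate by which this regimen will be compared with others. The go/no-go decision is not at stake.

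The PPS raises a related question. If completing the study means completing treatment, a patient who progresses on treatment cannot belong to it. A TTP or PFS curve drawn from first dose in that set would then contain no early events by construction.

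**Working it through.** **The plan's own figures.** I use section 14.1, which also records accrual. Section 14.8 states a different design; that is a separate matter and nothing here relies on it. Inputs are null 18%, target 40%, one-sided alpha 0.05 and power 80%.

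- n = [(1.645 × √(0.18 × 0.82) + 0.842 × √(0.40 × 0.60)) / 0.22]² = 22.53, rounded up to 23. This matches.
- 23 / 0.9 = 25.6, rounded up to 26. This matches.
- Patients who started treatment: 27 − 1 = 26. Room for non-evaluable patients: 26 − 23 = 3.

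**Effect of FAS exclusions.** Let r be the number of responders and k the treated non-responders outside the FAS. The FAS rate is r/(26 − k) and the all-treated rate is r/26, so the shift is r × k / [26 × (26 − k)]. The documents do not name an interval method. I use the exact (Clopper-Pearson) limits, which are the 2.5% quantile of Beta(r, n − r + 1) and the 97.5% quantile of Beta(r + 1, n − r).

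At the success threshold, r = 9:

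| Outside the FAS (k) | FAS rate | Exact 95% CI | Shift from 9/26 |
|---|---|---|---|
| 0 | 9/26 = 34.6% | 17.2 to 55.7 | none |
| 1 | 9/25 = 36.0% | 18.0 to 57.5 | +1.4 points |
| 2 | 9/24 = 37.5% | 18.8 to 59.4 | +2.9 points |
| 3 | 9/23 = 39.1% | 19.7 to 61.5 | +4.5 points |

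The shift grows with the number of responders. With k = 3, r = 10 gives 38.5% against 43.5% (30/598 = 5.0 points), and r = 15 gives 57.7% against 65.2% (45/598 = 7.5 points). At 9 responders the lower limit is below the 18% null in all 26 patients and above it in 23.

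**Effect on the decision.** The rule in 14.1 is a count, so adding non-responders to the denominator cannot reverse it. The exact one-sided probability of 9 or more at a true rate of 18% is 0.0142 with n = 23 and 0.0326 with n = 26. Both are below 0.05.

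**PPS, by comparison of sections.** Completion is not defined, and two readings are open.

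- *Completing treatment.* Section 14.3 sets completed patients against those who discontinued prematurely. Section 5.4 lists progression among the reasons to end therapy, 5.6 removes a patient from study when any of those reasons applies, and 5.5 places follow-up after removal. Section 10.4 counts progression, death and new therapy as TTP events. On this reading, patients who progress during treatment are outside the PPS, and its TTP and landmark PFS estimates are biased upward.
- *Completing the two-year follow-up in 5.5.* A patient who progressed could still be a completer, and the bias need not arise in this form.

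**The case against.** The strongest reply is that an evaluable denominator was planned openly. Section 14.1 sizes the trial on 23 evaluable patients of 26, which is a recognised choice in a single-arm phase II trial. Exclusions should also be few. Measurable disease is already an eligibility criterion (3.1), the calendar in section 9 schedules IgM on Day 1 of each cycle and at the off-treatment visit, and 7.5 asks for end-of-study procedures at withdrawal. A reader who knows the responder count could divide by 26 unaided.

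Most of this stands. It limits the size of the effect and rules out calling the FAS an error. Two things remain. The visit schedule protects the re-evaluation condition but not the one-cycle condition: a patient who stops during cycle 1 may be re-evaluated at the off-treatment visit and still be left out. And no section requires FAS exclusions to be listed or an all-treated interval to be given, so the reader's own division would rest on assuming that no excluded patient responded. Such a patient, re-evaluated with less than one cycle, would reverse the direction of the shift, but the case is remote.

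A reader might also infer that the population for TTP and landmark PFS is unspecified, because those sentences name none. The documents do not support that. The paragraph opens by assigning primary and secondary analyses to both the FAS and the PPS, section 1.3 lists PFS and TTP as secondary objectives, and 14.2 ranks the FAS first.

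**Conclusion.** The concern holds for the reported estimate. As written, the plan can raise the rate of VGPR or better and its interval, and it provides no all-treated figure against which to judge this. At 9 responders the shift is between 0 and 4.5 points. The upper figure assumes that all three patients in the 10% allowance fall outside the FAS and that none responded; the number actually excluded is not in the documents. More responders would give a larger shift.

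It would go too far to conclude that the success rule is compromised or that the FAS must be replaced as the primary set. The rule is a count and gives the same answer, and the evaluable set was prespecified. Accrual is described as complete and the trial is open-label, so changing the primary set now would raise its own questions.

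The PPS point is conditional on completion meaning completion of treatment, which the text favours but does not settle. I put no size on it. The only PFS figure in the documents (2.3) is a projected lower bound for a bortezomib regimen and is not stated to be a median. The PPS is a secondary assessment, and the FAS carries no completion condition.

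**What to change.** In section 14.7, add the rate of VGPR or better with an exact 95% CI in all patients who received at least one dose, which is the set 14.2 already defines for safety. Count patients not re-evaluated as non-responders, and report this rate beside the FAS rate. List each patient outside the FAS with the reason.

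Estimate TTP and landmark PFS without a completion condition, and do not present PPS versions of them as a check on the FAS. State in 14.2 what completing the study means wherever the term is kept.

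This needs a dated amendment to 14.2 and 14.7 before database lock and no new data. The one downside is that the all-treated rate may be slightly lower than the FAS rate.
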